7.2.5 TEAEs Leading to Discontinuation of Vaccination and Leading to Study Withdrawal

Separate tables and listings will be prepared for TEAEs leading to discontinuation of the vaccination, and TEAEs leading to withdrawal from the study.

7.2.6 Deaths

A large number of deaths is not expected in this study with healthy participants. A tabulation and participant data listing of all deaths will be provided.

7.3 Clinical Laboratory Tests

Clinical laboratory results for the lab analytes that appear in [Protocol EBS.AVA.212, Table 9](#) will be assigned by the central laboratory a toxicity grade (Grade 1=mild through Grade 4=potentially life-threatening).

Central laboratory measurements will be tabulated by treatment group (combined AV7909 and BioThrax) as follows:

- Observed values and changes from baseline of continuous laboratory variables (hematology, serum chemistry, and selected urinalysis parameters [e.g., specific gravity]) will be summarized using descriptive statistics (n, mean, SD, median, minimum, and maximum) by study visit and treatment group.
- Observed values of categorical laboratory analytes (e.g., urinary protein) and shifts from baseline (number and percentage) will be summarized by study visit and treatment group.
- Shift from baseline according to normal reference ranges (reported as ‘Low’, ‘Normal’, and ‘High’) will be summarized (number and percentage) by study visit and treatment group.
- Shift from baseline according to toxicity grading criteria grade (Grade 0, Grade 1-4) will be summarized (number and percentages) by study visit for analytes that appear in **Protocol EBS.AVA.212, Table 9**. Grade 0 includes all values within normal range or value not meeting criteria for toxicity of at least Grade 1.
- Frequency and percentage of participants with the highest grade of post baseline abnormal laboratory values according to toxicity grading criteria grade (Grade 1-4).

Laboratory data listing will be provided with all test results that are collected throughout the study per analyte for participants who have at least one abnormal result based on the reference range or with Grade 1 to Grade 4 based on toxicity grading criteria at any time of study. All applicable severity grades or abnormal flags displayed. A separate data listing will be provided with Grade 3 or above laboratory observations.

7.4 Vital Signs

Vital sign data will be assigned a toxicity grade (Grade 1=mild through Grade 4=potentially life-threatening) according to **Protocol EBS.AVA.212, Table 8**. For heartbeat and blood pressure, there are toxicity criteria for both increased and decreased levels; analyses for each direction (i.e., increased, decreased) will be presented separately.

Vital signs data will be summarized as follows:

- Observed values and changes from baseline by study visit and treatment group (AV7909 and BioThrax).
- Shift from baseline according to toxicity grading criteria grade (Grade 0, Grade 1-4) (number and percentages) by study visit and treatment group. Grade 0 includes all values not meeting criteria for toxicity of at least Grade 1.

All vital sign records will be provided in the participant data listings. This listing will include all results that are collected throughout the study for the analyte of interest, with all applicable severity grades displayed. A separate data listing will be provided with Grade 3 or above vital sign observations.

7.5 Physical Examinations

Complete and symptom-directed PE findings will be tabulated including number of participants with normal/abnormal PE findings by body system and study visit for each of the two treatment groups (AV7909 and BioThrax). Listings will be provided with all abnormal findings.

7.6 Prior and Concomitant Medications

Prior and concomitant medication information will be coded according to the World Health Organization's (WHO) WHODrug Global Dictionary. Data will be tabulated by Anatomical Therapeutic Chemical (ATC) classification level 4, medication preferred term, and treatment group (AV7909 and BioThrax) for prior and concomitant medications. A participant data listing of all medications will be provided.

Prior medications are those used from within 30 days before screening through the time of the first vaccination, while concomitant medications are those used after the first vaccination. For purposes of analysis, any medication with an end date between 30 days or less before date of screening and on or prior to the first vaccination, the date will be categorized as prior. Any medication which is ongoing or with an end date that is after the first vaccination date will be categorized as a concomitant medication. Partial dates will be imputed according to [Section 4.4](#). The summary will be sorted in descending order of percentage in the AV7909 group by drug class and drug name within a class. For drugs with the same frequency, sorting will be done alphabetically.

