After each vaccination by the unblinded member of site staff, the participant will be observed for at least 30 minutes (by a blinded member of site staff) for any adverse effects of vaccination, especially anaphylactic reactions. Site personnel will be trained in the recognition of early symptoms of anaphylactic reactions, a rare but potentially serious reaction to parenteral injections. Any such reactions must be reported as AEs (refer to [Section 9](#)). Sites must be ready to treat participants experiencing clinically significant dyspnea or hypotension, wheezing, or generalized urticarial reactions. Appropriate medical therapy for anaphylaxis will be administered, if indicated, including IM or SC epinephrine 1:1000, corticosteroids, diphenhydramine, bronchodilators, IV volume expansion, and/or oxygen. Participants will be evaluated and carefully monitored until complete resolution of any signs and symptoms, if they occur, to include transfer to the nearest emergency room if required.

For more detailed instruction on IP administration, refer to the Pharmacy Manual.

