6.5. Concomitant Therapy

Medication usage will be collected from participants and recorded in the participant's source documents and eCRF at Screening and at each study visit up through Day 64/EWV. After Day 64, medication usage will be recorded in the eCRF if involving an AE, SAE or AESI. Prior medications are those used from within 30 days before Screening through the time of the first vaccination, while concomitant medications are those used after the first vaccination. The medication name, dose, route, frequency, indication, and stop and start days/times for each new medication will be recorded. Refer to [Section 5.2](#) for prior medication usage that is disqualifying for study participation.

Prohibited and restricted concomitant medications during the study, which include anti-inflammatory or antipyretic medications, vaccines, immunomodulatory agents, antineoplastic agents, and immunoglobulins/other blood products, are summarized in [Table 4](#). The MM should be consulted for any questions about prohibited or restricted medication usage.

Table 4: Prohibited and Restricted Concomitant Medications

Type ^a	Examples ^b
Anti-inflammatory or antipyretic medication: prohibited within 24 hours before or after vaccination	Aspirin-containing medication, NSAIDs, acetaminophen-containing medication
Any commercially-available vaccine through two weeks after the last vaccination	BCG Vaccine, Engerix-B, Havrix, HEPLISAV-B, Imovax, influenza vaccines, Ixiaro, JE-Vax, Menomune-A/C/Y/W-135, Prevnar 13, Recombivax HB, Twinrix, Vaxchora, Vaqta
Immunomodulatory agents through Month 13 Note: inhalation use (eg, for seasonal allergies) is permitted.	Any systemic corticosteroids including, but not limited to, generic and brand names of: betamethasone, budesonide, cortisone acetate, dexamethasone, hydrocortisone, methylprednisolone, prednisolone, prednisone, triamcinolone Azasan (Salix Pharmaceuticals), CellCept (Roche Laboratories), Gengraf (Abbott), MICRhoGAM ultra-filtered (Ortho-Clinical), Myfortic (Novartis), Neoral (Novartis), Orthoclone OKT3 sterile solution (Ortho Biotech), Prograf (Fujisawa), Rapamune (Wyeth), Rituximab (Rituran, Mabthera; Genentech), Sandimmune (Novartis), Simulect (Novartis), Thymoglobulin (SangStat Medical Corp.), Zenapax (Roche Laboratories)
Antineoplastic agents through Month 13	Cyclophosphamides (Cytoxan, Neospar), Cytarabine (Cytosar-U, Ara-C, Cytosine arabinoside), Depocyt (Enzon), methotrexate, vincristine (Oncovin, Vincasar)

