10.6.6. Prior and Concomitant Medications

Medications will be coded according to the World Health Organization's (WHO) WHODrug Global Dictionary and daily dosages normalized. Data will be tabulated and listed by individual participant according to study period (prior medications taken before first IP administration, concomitant medications taken after first IP administration) and group.

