All adverse events experienced during the study period in both enrollments will be included in the summary tabulations. All AEs on or after the start date of treatment in the first enrollment will be considered as treatment emergent. It is worth noting that AEs may be reported under both subject numbers, but this will not impact incidence tables when the verbatim terms provided at the individual sites code to the same preferred term.

ADCM

All medications taken during the study period in both enrollments will be included in the summary tabulations. Prior medications will be those taken 30 days prior to start date of the first treatment associated with the first enrollment while concomitant medications will be those taken on or after the start date of the first treatment during the first enrollment. Note that medications can be reported under both subject numbers, but this will not impact incidence tables when the reported medications provided at the individual sites are coded to the same preferred name.

ADMH

Medical history data reported for either subject number will be included in summary tabulation unless the start date for the second enrollment clearly identifies that the history began after the first treatment of the first enrollment. An analysis flag will be added to flag only medical history which can contribute to the analysis.

ADDV

All protocol deviations experienced during the study period associated with either enrollment will be included in the summary tabulations.

ADSS

Refer to Population indicator variables in ADSL.

ADDD, ADIE

No impact on analysis.

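### The end-date rule in SAP 7.6 keeps a drug started and stopped on Day 1 after the first injection out of the concomitant-medication table, against its own definition

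*SAP*

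**What the plan says.** SAP 7.6 first gives a definition split at a point in time: prior use runs "through the time of the first vaccination, while concomitant medications are those used after the first vaccination". Protocol 6.5 has the same split, "while concomitant medications are those used after the first vaccination", and Protocol 10.6.6 tabulates by "prior medications taken before first IP administration, concomitant medications taken after first IP administration".

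SAP 7.6 then sets a separate rule for analysis. The prior class takes "any medication with an end date between 30 days or less before date of screening and on or prior to the first vaccination" (the end of that sentence is garbled, but the assignment to prior is clear). The other class is given by: "Any medication which is ongoing or with an end date that is after the first vaccination date will be categorized as a concomitant medication". Neither sentence uses the start date or start time.

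For the four people who enrolled at two sites, SAP Appendix IV (ADCM) uses another rule: "concomitant medications will be those taken on or after the start date of the first treatment during the first enrollment".

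The data for a time-based split are collected. Protocol 6.5 says that "stop and start days/times for each new medication will be recorded", and Protocol 6.4 has the date and time of each vaccination recorded.

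**The concern.** Drug use between the first injection and midnight on Day 1 is use after vaccination under every definition in the two documents, and the plan foresees it. Protocol 6.1.2 requires at least 30 minutes of observation after each injection and states: "Appropriate medical therapy for anaphylaxis will be administered, if indicated, including IM or SC epinephrine 1:1000, corticosteroids, diphenhydramine, bronchodilators". E-diary entries begin on the evening of Day 1 and ask about pain and fever medication, and any such use must be copied to the eCRF (Protocol 6.5 and 8.3.5.1).

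If such a drug also stops on Day 1, the analysis rule puts it with pre-treatment medication. The safety outputs can then disagree. Under SAP 7.2.1 an adverse event that starts on the vaccination date is treatment-emergent, so a Day 1 reaction would be a TEAE while the drug given for it that day is tabulated as prior. A programmer also cannot satisfy the SAP 7.6 definition, the SAP 7.6 rule and Appendix IV together.

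**Working it through.** The plan gives no figure to reproduce. The check is to run test records through each rule, with a first vaccination assumed at 10:00 on Day 1. The clock time is illustrative; only the order of events matters.

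Rules compared:

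- **R1**, SAP 7.6 rule read by date: concomitant if ongoing or end date > vaccination date; otherwise prior.
- **R2**, SAP 7.6 rule with the prior limit read by clock time: prior if end time ≤ vaccination time; concomitant if ongoing or end date > vaccination date.
- **R3**, definition sentence in SAP 7.6, Protocol 6.5 and 10.6.6: concomitant if ongoing or used after the vaccination time; otherwise prior.
- **R4**, SAP Appendix IV: concomitant if taken on or after the vaccination date.

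| Record | R1 | R2 | R3 | R4 |
|---|---|---|---|---|
| Day 1, 07:00 only (before the dose) | prior | prior | prior | concomitant |
| Day 1, 15:00 only (after the dose) | **prior** | **neither** | concomitant | concomitant |
| Started Day 1 at 15:00, ended Day 2 | concomitant | concomitant | concomitant | concomitant |
| One day only, Day 15 | concomitant | concomitant | concomitant | concomitant |
| Started before screening, ongoing | concomitant | concomitant | concomitant | concomitant |

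What follows:

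1. The second record is the only one on which the SAP 7.6 rule departs from the SAP 7.6 definition. Its end date equals the vaccination date, so it fails the test for an end date after that date.
2. Reading the prior limit by clock time does not rescue it. The concomitant test is explicitly by date, so the record drops out of both classes.
3. For records with complete dates the error runs one way. An end date after the vaccination date always means use after vaccination, so the rule can remove records from the concomitant class but cannot add any.
4. Appendix IV gets the second record right but the first wrong: a drug taken only before the injection on Day 1 becomes concomitant. It therefore cannot simply be copied into SAP 7.6.
5. Elsewhere the SAP does use clock time for this boundary: SAP 3.4 defines baseline by the date and time of the first vaccination.

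**The case against.** The strongest reply is that little depends on this table, and most of that reply stands.

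- **No comparison by dose is planned.** SAP 7.6 tabulates by ATC level 4, preferred term and treatment group, with no split by vaccination. A reader might infer that an AV7909-versus-BioThrax comparison of drug use after dose 1 is biased. No such comparison exists, and the documents give no Day 1 use by arm from which to infer a direction.
- **Participants are counted, not records.** SAP Appendix I bases percentages on participants. Someone who takes the same drug again on a later date is still counted as a concomitant user. One-day use after doses 2 and 3 is classed correctly.
- **The number affected may be small.** Protocol Table 4 prohibits anti-inflammatory and antipyretic drugs within 24 hours of vaccination. A reader might put an assumed use rate on the 3850 participants and report hundreds of misplaced records. No rate in the documents supports that. The prohibition does not, however, cover rescue drugs such as epinephrine or diphenhydramine.
- **Reactogenicity is not read against this table.** A reader might infer that dose 1 pain and fever grades are interpreted with an incomplete treatment record. SAP 7.7.1 summarizes e-diary grades without reference to the medication tables.
- **The information is not lost.** SAP 7.6 lists every medication, reactions seen in the observation period must be reported as AEs (Protocol 6.1.2), and deviations are summarized and listed (SAP 5.2).
- **Appendix IV concerns four people**, so that conflict alone would be minor.

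None of this removes the contradiction between the SAP 7.6 rule and its own definition, or makes the resulting table entry correct.

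**Conclusion.** The rule is wrong as written: followed literally, it gives incorrect entries in a planned safety table. The consequence is limited. It touches only the descriptive prior and concomitant medication tables, and there only participants whose sole use of a given drug after the first injection ended on the day of dose 1. For them the concomitant count is too low and, on the date reading, the prior count may be too high.

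How many are affected, and whether the arms differ, cannot be computed from the documents. No primary or secondary endpoint uses the label. Per Protocol exclusion for medication rests on the Sponsor's own assessment (SAP 3.2), not on this class. The conclusion rests on the wording of SAP 7.6 alone; it assumes only that some drugs will be started and stopped on Day 1 after the injection.

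**What to change.** Replace the analysis rule in SAP 7.6 with one that implements its definition:

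- Concomitant: the start or stop date/time is after the date/time of the first vaccination, or the drug is ongoing.
- Prior: stopped at or before the date/time of the first vaccination, within the existing look-back period.
- If the date is Day 1 and a missing time leaves the order unresolved: concomitant.

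With complete times the stop time alone decides. The start condition matters when only the stop time is missing. Apply the same rule in Appendix IV (ADCM), anchored to the first vaccination of the first enrollment, so that one derivation serves all participants.

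The cost is a few lines of SAP text and one change to the ADCM derivation, with no new data. The downside is that a few drugs taken before the injection on Day 1, without a recorded time, would be counted as concomitant; a table footnote can say so.

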7.7 Other Safety Analyses

7.7.1 E-diary Reactogenicity

E-diary reactogenicity data will be summarized with number and percentage of participants with the highest severity grade for each symptom of solicited systemic reactions (tiredness, muscle ache, headache, and fever) and injection site reactions (warmth, tenderness, itching, pain, arm motion limitation, redness, induration, swelling, and bruising) by severity grade and treatment group post each vaccination. Severity of fever will be attributed programmatically using oral temperature measurement reported in the e-diary according to grading scale for fever in [Protocol EBS.AVA.212, Table 8](#).

Stacked bar charts with color coded severity and participant listings will be provided for each symptom of systemic and injection site reactions.

7.7.2 In-clinic Reactogenicity

In-clinical reactogenicity data will be summarized in the similar manner as those for e-diary reactogenicity, except for fever (oral temperature) which will be reported and presented as vital sign observations at 30 minutes post vaccinations.

All in-clinical reactogenicity data will be provided in the data listings.

7.7.3 E-diary Compliance

E-diary compliance will be summarized by vaccination and treatment group (AV7909 and BioThrax). Degree of compliance for a participant and vaccination will be calculated based on the expected total number of diary days, including extra days if there was an ongoing reaction, times the number of questions per day. The participant-level compliance percentage will be calculated for each vaccination, and then summarized using descriptive statistics.

7.7.4 Auto-antibody Testing and TSH Assessment

Auto-antibody testing of RF, ANA and anti-dsDNA antibodies and TSH assessment will be tabulated with negative/positive results by study visit and treatment group (AV7909 and BioThrax) and subject listing will be provided with all test results that are collected throughout the study per analyte for participants who have at least one abnormal result at any time of study.

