If the original (retested sample) or repeat laboratory value is Grade 3 or higher, this will be considered an AE and will be recorded by the PI on the AE eCRF. Any other clinical laboratory abnormalities must also be reported as AEs if considered by the PI or designee to be a clinically significant change from baseline. As toxicity grading is being used in this study to evaluate and record AE severity (refer to [Section 9.2.1](#)), the lab toxicity grade is to be assigned as the AE toxicity grade when reporting on the AE eCRF. If the lab analyte does not have toxicity grading criteria specified in [Table 9](#), then the PI or designee will use the grading criteria for “illness or clinical AE” in [Table 8](#) to assign the AE toxicity grading. If an abnormal laboratory test result is a sign of a disease or syndrome, the disease or syndrome will be recorded as the AE/SAE and not the abnormal laboratory result. Clinical laboratory abnormalities may trigger study halting rules (see [Section 7.1](#)) and will require discontinuation of vaccinations in an individual participant if considered associated with vaccination (see [Section 7.3](#)).

Table 7: Screening/Safety Clinical Laboratory Tests

Hematology -Basophils -Eosinophils -Hematocrit -Hemoglobin -Lymphocytes -Monocytes -Neutrophils -Platelets -RBC count -WBC count Serum Chemistry -ALP -ALT -AST -Bilirubin, Total -BUN -Creatinine -Glucose, nonfasting	Urinalysis -Appearance -Bilirubin -Color -Glucose -Ketones -Leukocyte esterase -Nitrite -Occult blood -pH -Protein -Specific gravity -Urobilinogen -Microscopic examination (only if protein, nitrite, leukocyte esterase, or occult blood results are positive) Additional Tests -FSH (only in women having > 12 consecutive months without menses to confirm postmenopausal status) -Serum/urine pregnancy test (WOCBP only; also suspected postmenopausal women at Screening only) -TSH	Viral Serology: -anti-HCV antibody -anti-HIV antibody -HBsAg Urine Drug Screen: -Amphetamines -Barbiturates -Benzodiazepines -Cannabinoids -Cocaine -Opioids Autoantibodies -RF -ANA -anti-dsDNA antibodies
---	---	--

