2.2.3.2 Clinical Laboratory Assessments

All analytes to be tested during screening/safety clinical laboratory tests are specified in [Protocol EBS.AVA.212, Table 7](#).

The following assessments will be performed at Screening only:

- Urine drug screen (refer to Protocol EBS.AVA.212, Table 7 for analytes)
- Serologic testing (HIV-1/HIV-2 antibodies, HBV surface antigen, and HCV antibody). Confirmatory testing will be performed on any samples that test positive for either HIV or HCV; no additional blood/serum will be required for this confirmatory testing.
- FSH test to confirm postmenopausal status in women having > 12 consecutive months without menses (refer to [Protocol EBS.AVA.212, Section 5.1](#)).

Pregnancy testing will be performed at all visits including EWV. Female participants who are confirmed at Screening to be surgically sterile (refer to Protocol EBS.AVA.212, Section 5.1) are exempt from pregnancy testing. Vaccine will not be administered to any subject who tests positive for pregnancy.

Blood and urine samples for safety clinical laboratory testing (hematology, serum chemistry, urinalysis) will be collected at Screening and Day 29 as well as at the EWV if the EWV occurs before Day 29. Refer to Protocol EBS.AVA.212, Table 7 for the complete list of analytes to be tested. Blood samples for auto-antibody assessment of RF, ANA and anti-dsDNA antibodies and TSH will be taken at Day 1 prior to vaccination, Day 64/EWV, and at the time of unscheduled visit(s) if warranted from participant report(s) of potential AESI(s) at the safety follow-up phone call(s).

All samples will be sent to the central laboratory for analysis, except urine for pregnancy testing in women of childbearing potential (WOCBP), which will be performed at the site and results documented in the eCRF.

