3.3 Analysis Time Points

Participant visits occur on protocol-specified days with associated visit windows. For purposes of data analysis, if the study day of assessment falls within the visit window, the corresponding analysis visit will be assigned as specified in Table 3 for vaccination, immunogenicity (TNA) testing, clinical laboratory data, vital signs, physical examinations, auto-antibiotic testing, and TSH assessment.

Table 3 Analysis Windows for Vaccination, Immunogenicity (TNA) Testing, Clinical Laboratory Data, Vital Signs, Physical Examinations, Auto-antibiotic Testing, and TSH Assessment

Analysis Visit	Nominal Day	Lower Limit	Upper Limit
Baseline	NA	-28	1, prior to the first vaccination
Day 1	1	1, since the first vaccination	1, since the first vaccination
Day 15	15	14	16
Day 29	29	27	31
Day 64	64	61	67

Out-of-window immunogenicity testing results will be excluded from the analyses for lot consistency and immunogenicity. Data at unscheduled visits might not be presented in the by-visit summary analyses, but will be included in the summary tables by maximum toxicity grade or abnormality and data listings. On vaccination days, vital signs will be taken before vaccination and at 30 minutes (± 5 min) postvaccination, and therefore data will be tabulated for pre- and post-vaccinations, as appropriate.

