3.5 Selection of Data in the Event Multiple Records in an Analysis Window

For clinical laboratory data, vital signs, physical examinations, auto-antibiotic testing, and TSH assessment, if multiple valid non-missing observations exist in an analysis window for a specific visit, a single value will be chosen in the by-visit summary analyses based on the following rules:

- For baseline, the last available record prior to the date and time of the first vaccination will be selected.
- For post baseline visits,
 - if the analysis values are numeric and the toxicity grades are available, the record with the highest toxicity grade will be selected;
 - if the analysis values are numeric and the toxicity grades are identical or not available, the average (arithmetic mean) will be used;
 - if the analysis values are categorical, the most conservative value will be selected (e.g., abnormal will be selected over normal).

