 - If not otherwise specified, mean, geometric mean, standard deviation, median, minimum, maximum, and CI values will be formatted with the same number of decimals found in the raw data.
 - One decimal point or two significant digits (e.g., min 0.032 max 18.0) is presented for TNA NF₅₀.
 -
 - Geometric mean ratio will be formatted with two decimal places.
- P-values will be 2-sided and presented with 2 significant digits, i.e. 0.45, 0.045. P-values less than 0.001 will be presented as “< 0.001”.
- Unless otherwise specified, CIs are two-sided with 95% confidence.
- For numerical variable data summary, align decimal point of each statistics across rows. For 95 CI, align the ‘,’ with the decimal point of above statistics.

	Group 1 (N=xxx)	Group 2 (N=xxx)	Group 3 (N=xxx)
Parameter 1			
n	xx	xx	xx
Mean	xx.x	xx.x	xx.x
SD	xx.xx	xx.xx	xx.xx
Median	xx.x	xx.x	xx.x
Min, Max	xx, xx	xx, x	xx, xx

- For categorical variables, the number and percentage of responses will be presented in the form XX (XX.X), where the percentage is in the parentheses. Percentages will be calculated using a denominator of all participants in a specified analysis population (and present at the analyzed visit in by-visit summaries). The denominator will be specified in a footnote to the tables for clarification where necessary. All percentages will be rounded to one decimal place. Unless otherwise specified, the “N=xx” under each column header will represent the number of participants in that group, and all percentages below will be based on this number. Align count (integer) and first parenthesis across each row. Align decimal place of percentages and zero frequencies (present as 0, no percentage).
- Each level of indentation within a table takes a space of 2 characters.

Group 1 (N=xxx) n (%)	Group 2 (N=xxx) n (%)	Group 3 (N=xxx) n (%)
xx (100.0)	xx (100.0)	xx (100.0)
0	xx (xx.x)	x (x.x)
xx (xx.x)	0	xx (xx.x)
xx (x.x)	x (x.x)	xx (xx.x)
x (x.x)	x (x.x)	0

3. Listing

Convention

- Listings should be

sorted by site, study group, subject numbers and (if applicable) visit day/time or sequence number. Values from repeat tests and unscheduled visits should be presented chronologically with values from scheduled visits.

- In a listing, the subject number should be displayed only once for the subject with multiple records. If a subject's records run into multiple pages, display the subject number once for every page.

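### SAP 7.7.4 names no newly-positive (shift) table for RF, ANA and anti-dsDNA, summarises TSH as negative/positive, and leaves unclear whether the SAP 7.3 shift tables apply

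*SAP*

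**What the plan says.** SAP 7.7.4 (Auto-antibody Testing and TSH Assessment) gives one rule for all four tests: "Auto-antibody testing of RF, ANA and anti-dsDNA antibodies and TSH assessment will be tabulated with negative/positive results by study visit and treatment group". It adds a listing: "subject listing will be provided with all test results that are collected throughout the study per analyte", restricted to participants with at least one abnormal result. SAP Appendix I has listings "sorted by site, study group, subject numbers and (if applicable) visit day/time or sequence number". Protocol 10.6.7.2 asks only that auto-antibody results be listed and tabulated.

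The samples are paired. Protocol 8.3.2 and SAP 2.2.3.2 take blood for RF, ANA, anti-dsDNA and TSH on Day 1 before vaccination and at Day 64 or the early withdrawal visit (EWV).

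SAP 7.3 (Clinical Laboratory Tests) has a fuller rule. It opens with "Central laboratory measurements will be tabulated by treatment group (combined AV7909 and BioThrax) as follows" and goes on to shifts from baseline for categorical analytes and low/normal/high shifts against reference ranges.

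The documents point both ways on whether 7.3 covers the auto-antibodies and TSH:

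- For: the protocol lists them in "Table 7: Screening/Safety Clinical Laboratory Tests", and SAP 2.2.3.2 describes them under laboratory assessments and says "All samples will be sent to the central laboratory for analysis", urine pregnancy tests excepted.
- Against: SAP 3.5 names them as separate items ("For clinical laboratory data, vital signs, physical examinations, auto-antibiotic testing, and TSH assessment", where auto-antibody is misprinted), SAP 3.3 does the same, and 7.7.4 gives them a rule of their own.

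**The concern.** Protocol 2.3.2 explains why the samples are drawn. CpG adjuvants might trigger autoimmune disease, and earlier trials of this adjuvant reported transient anti-dsDNA elevations, positive ANA and mild RF elevations after vaccination, usually resolving and without symptoms. What a paired sample adds is the number of participants negative before vaccination and positive afterwards, by arm. The table in 7.7.4 gives two separate prevalences instead.

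Participants who are already positive are not screened out. Exclusion criterion 9 relies on medical history and physical examination, and the first auto-antibody sample is the Day 1 one. Day 64 positivity therefore mixes old and new positives.

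For TSH the difficulty is more basic. Neither document defines a positive TSH, and Protocol Table 9 has no TSH grade. A programmer would have to invent a cut-off, and a single abnormal category would merge low with high values.

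Without a planned table, the count of new positives would have to be assembled from the listing after the data are seen.

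**Working it through.** **1. What counts by visit leave open.** Let N be the participants tested at both visits, pB the proportion positive at Day 1 and pD the proportion positive at Day 64. The number newly positive lies between N × max(0, pD − pB) and N × min(pD, 1 − pB). N = 3000 is the AV7909 safety size in SAP 2.4. The documents give no positivity rates, so those below are assumed.

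| Day 1 / Day 64 positive | Newly positive, range |
|---|---|
| 5% / 5% | 0 to 150 |
| 10% / 10% | 0 to 300 |
| 15% / 15% | 0 to 450 |
| 10% / 12% | 60 to 360 |

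A Day 1 by Day 64 cross-tabulation gives the exact number.

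**2. Precision of the comparison between arms.** Inputs: n1 = 3000 (AV7909) and n2 = 550 × 0.90 = 495 (BioThrax, the same 10% drop-out assumed). Assumed rates: baseline positivity p; reversion r of 0 or 20%; new positives a = 2% or 3% with AV7909 and b = 1% with BioThrax.

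- Day 64 positivity is q1 = p(1 − r) + (1 − p)a with AV7909, and q2 is the same with b in place of a. The half-width is 1.96 × √[q1(1 − q1)/n1 + q2(1 − q2)/n2].
- For new positives the proportions are a and b, and the sizes are n1(1 − p) and n2(1 − p).
- Example at p = 10%, r = 0, a = 3%: q1 = 0.127 and q2 = 0.109. The Day 64 half-width is 1.96 × √(0.127 × 0.873/3000 + 0.109 × 0.891/495) = 2.99 points. For new positives it is 1.96 × √(0.03 × 0.97/2700 + 0.01 × 0.99/445.5) = 1.13 points.

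| Baseline positive | Day 64 positivity, half-width (points) | Newly positive, half-width (points) | Ratio |
|---|---|---|---|
| 0% | 1.01-1.07 | 1.01-1.07 | 1.00 |
| 1% | 1.31-1.41 | 1.01-1.07 | 1.26-1.35 |
| 5% | 2.09-2.30 | 1.04-1.10 | 1.93-2.19 |
| 10% | 2.72-2.99 | 1.06-1.13 | 2.43-2.80 |
| 20% | 3.56-3.87 | 1.13-1.19 | 2.99-3.43 |

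The example in rounded counts: new positives 81/2700 = 3.0% (exact 95% CI 2.39-3.72) against 4/446 = 0.9% (0.24-2.28), Newcombe difference 2.1 points (0.6 to 3.0). Day 64 positivity 381/3000 against 54/495 gives 1.8 points (−1.5 to 4.5).

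**3. Early-withdrawal samples.** Protocol 8.1.7 limits haematology, chemistry, urinalysis and TNA at the EWV by timing, but not auto-antibodies or TSH. Under SAP 3.3, "if the study day of assessment falls within the visit window, the corresponding analysis visit will be assigned as specified in Table 3". Table 3 follows from the visit windows: 15 ± 1 = 14-16, 29 ± 2 = 27-31, 64 ± 3 = 61-67. It has no EWV row. Of EWV Days 2-63 (62 days):

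- 3 (Days 61-63) map to Day 64;
- 3 + 5 = 8 map to Day 15 or Day 29, visits with no scheduled auto-antibody sample;
- 62 − 11 = 51 map to no visit.

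An EWV held on Days 64-67 would also map to Day 64. These are calendar days, not samples. At the planned 10% drop-out the ceiling is 3300 × 0.10 = 330 AV7909 and 550 × 0.10 = 55 BioThrax participants.

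**The case against.** The strongest reply is that SAP 7.3 already supplies what is asked. These are central laboratory measurements, and 7.3 plans shifts for them. A reader might therefore infer either that nothing is missing or, at the other extreme, that the SAP contains no shift analysis for these tests. The documents establish neither. The separate naming in 3.3 and 3.5 and the dedicated rule in 7.7.4 weigh against 7.3 applying, and its bullet on continuous variables names only haematology, serum chemistry and selected urinalysis. But nothing excludes 7.3. What stands is that 7.7.4 names no shift table and the reach of 7.3 is unstated.

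A second reply is that new positives can be counted from the listing, which shows every result for anyone with an abnormal value, sorted by study group. That is true if abnormal includes positive and few Day 1 samples are missing. It remains a hand count with a denominator nobody specified in advance.

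Third, Day 1 and Day 64 prevalence by randomised arm already permits a valid comparison, and it targets a different quantity from new positivity. Both statements are correct. The shift table adds a direct count and, depending on baseline rates, precision.

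Fourth, these data are secondary in weight. SAP 7.2.4 analyses DSMB-adjudicated autoimmune events separately, auto-antibody conversion is not a named endpoint, and 7.7.4 satisfies Protocol 10.6.7.2. This limits the importance of the point but does not remove it. The TSH wording may simply be loose, since the same sentence uses abnormal for the listing, but it still has to be made programmable.

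**Conclusion.** The point holds as a recommended improvement. The paired RF, ANA and anti-dsDNA results are reduced to counts by visit that cannot show conversion, and negative/positive has no stated meaning for TSH. Whether SAP 7.3 repairs either is unclear from the text.

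Its size depends on a rate the documents do not give. Comparing new positives instead of Day 64 positivity gains nothing in precision at 0% baseline positivity, little at 1%, and about two- to three-fold at 5-20%. All rates in that calculation are assumptions. With samples only at Day 1 and Day 64, a shift table shows conversions still present at Day 64, so transient ones would be missed.

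Two stronger inferences should be resisted:

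- It would be wrong to say that every early-withdrawal sample outside Days 61-63 is unplaced. Table 3 also assigns Days 14-16 and 27-31, and its Day 64 window runs to Day 67. The gap is a minor one of missing detail, abnormal results would still be listed, and the ceiling of 330 and 55 is likely too high. It counts all planned drop-out as early withdrawals with an EWV, whereas participants who only stop vaccination are encouraged to stay and give a Day 64 sample.
- Nor do the documents support a claim that autoimmune safety goes unanalysed.

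**What to change.** In SAP 7.7.4:

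1. Add a Day 1 to Day 64 shift table by arm for RF, ANA and anti-dsDNA, with the proportion newly positive among participants negative at Day 1 and its exact 95% CI. Keep it descriptive. If a difference between arms is wanted, the Newcombe method of SAP 6.2.2.2 can be used without a test.
2. Replace negative/positive for TSH with observed and change-from-baseline values and a low/normal/high shift.
3. State whether SAP 7.3 applies to these tests. If it does, a cross-reference covers much of items 1 and 2.
4. As a minor clarification, report EWV auto-antibody and TSH results separately from Day 64, since they come at varying times after dosing, and do not let them fall under Day 15 or Day 29.

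The cost is SAP wording and a few descriptive tables from data already collected. No extra sampling or hypothesis test is needed.
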